Study Protocol

Preoperative Psychotherapy and Its Effects on Anxiety, Hemodynamics, and Pain in Living Kidney Donors (PREPSY-KD)

Protocol Version: 1.0

Protocol Date: November 2023

Organization's Protocol ID: KAEK-840

1. Background and Rationale

Living kidney donation is an essential treatment modality for end-stage renal disease (ESRD). Donor nephrectomy, while performed in healthy individuals, is associated with significant psychological stress due to hospitalization, surgical anticipation, anesthesia concerns, and uncertainty regarding recovery. Preoperative anxiety has been shown to negatively affect postoperative pain, hemodynamic stability, anesthetic requirements, and overall recovery.

Psychotherapeutic interventions such as psychoeducation, guided imagery, and diaphragmatic breathing exercises have demonstrated benefits in reducing perioperative anxiety and improving physiological parameters. However, there is limited prospective evidence evaluating the effect of structured preoperative psychiatric consultations on anxiety, hemodynamic responses, and postoperative pain in living kidney donors.

This study aims to assess whether a brief standardized psychiatric consultation administered before donor nephrectomy affects perioperative anxiety levels, intraoperative hemodynamics, and postoperative pain outcomes.

2. Study Objectives

Primary Objective

- To evaluate the effect of preoperative psychiatric consultation on postoperative pain scores measured via the Visual Analog Scale (VAS) at predefined postoperative time points.

Secondary Objectives

- To compare preoperative and postoperative anxiety levels between intervention and control groups using the Beck Anxiety Inventory (BAI).
 - To compare intraoperative hemodynamic parameters (heart rate, systolic and diastolic blood pressure, SpO₂) between groups.
 - To evaluate postoperative oxygen saturation trends.
 - To assess postoperative opioid consumption and antiemetic requirements.
-

3. Study Design

- **Study Type:** Interventional

- **Design:** Prospective, randomized, parallel-assignment clinical trial
- **Number of Arms:** 2 (Intervention vs. Standard Care)
- **Masking:** Single-blind (Outcomes Assessor)
- **Allocation:** Randomized
- **Primary Purpose:** Supportive Care
- **Study Duration:** November 2023 – November 2024

Randomization was performed via sealed envelopes during preoperative evaluation. Outcome assessors evaluating VAS scores were blinded to group allocation.

4. Study Population

Inclusion Criteria

- Age \geq 18 years
- ASA physical status I-II
- Voluntary participation with signed informed consent
- Living kidney donor scheduled for elective donor nephrectomy

Exclusion Criteria

- Diabetes mellitus diagnosis
 - Development of postoperative delirium
 - Known psychiatric illness or psychiatric medication use
 - Neurological or musculoskeletal disorders
 - Chronic pain or chronic pain treatment
 - Recent significant psychological trauma
 - Analgesic drug use within the last month
-

5. Interventions

Intervention Group: Preoperative Psychiatric Consultation

Participants received a standardized 15-minute psychiatric session one hour before surgery under psychiatrist supervision, including:

- History-taking (3–5 minutes)
- Psychoeducation regarding anxiety and surgical preparation (3–5 minutes)
- Diaphragmatic breathing exercises (1–3 minutes)
- Guided imagery techniques (3–5 minutes)

The intervention was delivered by an anesthesiologist trained by a psychiatrist through structured educational sessions.

Control Group: Standard Preoperative Care

Participants received routine preoperative evaluation. No psychiatric intervention was performed.

6. Outcome Measures

Primary Outcome

- Postoperative Pain Score (VAS 0–10)**

Time Frame: Postoperative 30 minutes, 2 hours, 6 hours, 12 hours, 24 hours, and 48 hours.

Secondary Outcomes

- State Anxiety Score (Beck Anxiety Inventory, 0–63)**

Time Frame: 30 minutes preoperatively, postoperative 24 hours, postoperative 48 hours.

- Postoperative SpO₂ Levels (%)**

Time Frame: Postoperative 30 minutes, 2 hours, 6 hours, 12 hours, 24 hours, 48 hours.

- Intraoperative Heart Rate (beats/min)**

Time Frame: Pre-induction, 30 minutes after induction, 1 hour after induction.

- Intraoperative SpO₂ Levels (%)**

Time Frame: Pre-induction, 30 minutes after induction, 1 hour after induction.

- Intraoperative Systolic Blood Pressure (mmHg)**

Time Frame: Pre-induction, 30 minutes after induction, 1 hour after induction.

- Intraoperative Diastolic Blood Pressure (mmHg)**

Time Frame: Pre-induction, 30 minutes after induction, 1 hour after induction.

- Total Opioid Consumption (mg)**

Time Frame: Intraoperative period and postoperative first 24 hours.

- Antiemetic Use (Yes/No, mg)**

Time Frame: Intraoperative period and postoperative first 6 hours.

7. Data Collection Procedures

Data will be collected at standardized time points by trained staff members. Hemodynamic parameters will be retrieved from anesthesia monitoring records. Pain scores will be evaluated using a 10 cm Visual Analog Scale. Anxiety assessments will be performed by a blinded outcomes assessor.

8. Statistical Analysis Plan

- Categorical variables: χ^2 or Fisher's exact test
- Continuous variables with normal distribution: Independent samples t-test
- Non-normal distribution: Mann-Whitney U test
- Repeated measurements: Repeated Measures ANOVA or Friedman test
- Correlations: Pearson or Spearman coefficients
- Significance threshold: $p < 0.05$
- Software: SPSS 15.0 version

All analyses will be performed per-protocol.

9. Ethical Considerations

- Ethics Committee Approval: **Akdeniz University Clinical Research Ethics Committee**
Approval Number: **2023-KAEK-20 / 840**
- Board Status: Approved
- Participation is voluntary; written informed consent obtained from all donors.
- No investigational drug or device used.
- Risks are minimal and limited to standard perioperative care.

10. Study Timeline

- Start of enrollment: November 1, 2023
- Primary completion: October 1, 2024
- Study completion: November 1, 2024

11. Data Management and Monitoring

A formal Data Monitoring Committee is not required due to minimal-risk behavioral intervention and absence of investigational medicinal products.

All data will be anonymized and stored securely following institutional data protection guidelines.

12. Publication Plan

Findings will be submitted to peer-reviewed anesthesiology and transplant journals and may be presented at national and international conferences.

13. References

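### Postoperative delirium is an exclusion criterion that can only be met after randomisation and surgery; with per-protocol-only analysis, its natural effect is to remove randomised donors

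*Combined protocol and SAP*

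**What the plan says.** Section 4 (Exclusion Criteria) has seven items. Six describe a donor's state or history before surgery. The other is "Development of postoperative delirium".

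On timing, Section 3 states: "Randomization was performed via sealed envelopes during preoperative evaluation". Section 5 adds, for the intervention arm: "Participants received a standardized 15-minute psychiatric session one hour before surgery".

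On the analysis set, Section 8 has one sentence: "All analyses will be performed per-protocol". It does not define the per-protocol set, and it plans neither an analysis of all randomised donors nor a sensitivity analysis.

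The documents do not define delirium or say how, when or by whom it is assessed. They do not say what happens to data already collected from a donor who develops it. Nothing says that such a donor stays in the analysis.

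**The concern.** An exclusion criterion normally decides who may be randomised. This one cannot, because nobody can meet it until allocation and surgery are over. For a donor already randomised and operated on, the main thing an exclusion criterion can still do is end follow-up or remove the donor from the analysis, and a per-protocol-only plan gives it the means.

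Two things are at stake. First, the arms compared would be selected on something that happened after randomisation, so the protection that randomisation gives the VAS comparison is weakened. Second, a donor removed whole takes along measurements that delirium gives no reason to distrust.

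Removal is also open to discretion. Section 3 says of pain "Outcome assessors evaluating VAS scores were blinded to group allocation" and Section 7 says of anxiety "Anxiety assessments will be performed by a blinded outcomes assessor". Neither says who judges delirium, or whether that person is unaware of the arm.

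**Working it through.** The documents give no sample size, delirium rate, VAS difference or SD, so there is no planned figure to reproduce. The check has four steps.

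**1. Order of events** (Sections 3, 4 and 5). Intervention arm: randomisation, session, surgery, then possible delirium. Control arm: the same without the session. In both arms the criterion can only be met after randomisation and surgery.

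**2. What delirium can affect** (schedule in Section 6).

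- VAS: 6 readings, all postoperative self-reports.
- BAI: 3 readings, of which 2 are postoperative self-reports.
- Postoperative SpO2: 6 readings.
- Intraoperative heart rate, SpO2, systolic and diastolic pressure: 4 × 3 = 12 readings.

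The total is 6 + 3 + 6 + 12 = 27. Postoperative self-reports number 6 + 2 = 8. The other 27 − 8 = 19 (12 intraoperative, 6 SpO2, 1 preoperative BAI) do not rest on postoperative self-report, and neither do the opioid and antiemetic data. The intraoperative readings and the preoperative BAI are complete before postoperative delirium can begin.

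**3. Size of the shift in VAS.** Let mC and mI be the mean VAS of donors without delirium in the control and intervention arms, pC and pI the delirium risks, and dC and dI the VAS excess of delirious donors. Define benefit as control minus intervention.

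- All randomised: (mC + pC·dC) − (mI + pI·dI)
- After removal: mC − mI
- Change caused by removal: −(pC·dC − pI·dI)

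With a common excess d in both arms, the change is −(pC − pI)·d. All inputs below are assumptions.

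| pC, pI | d = 1 | d = 2 | d = 3 |
|---|---|---|---|
| 5%, 5% | 0 | 0 | 0 |
| 5%, 2% | −0.03 | −0.06 | −0.09 |
| 5%, 1% | −0.04 | −0.08 | −0.12 |
| 10%, 5% | −0.05 | −0.10 | −0.15 |
| 1%, 5% | +0.04 | +0.08 | +0.12 |

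For risk gaps of 0 to 5 points and d of 1 to 3, the size is therefore 0 to 0.05 × 3 = 0.15 points on the 0–10 scale. The sign depends on which arm has more delirium, and it reverses if delirious donors score lower. Equal risks give zero only if the excess is also equal: at 5% in both arms with excesses of 3 and 1, the size is 0.05 × 3 − 0.05 × 1 = 0.10.

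**4. Whether the planned tests would keep these donors.** Suppose the donor stays in but some VAS readings could not be obtained. Section 8 assigns repeated measurements to repeated measures ANOVA or Friedman. In standard form both need every reading, so the donor drops out again. The two-group line, "Continuous variables with normal distribution: Independent samples t-test", with Mann-Whitney as the alternative, keeps each available reading if applied at each time. Take 5% versus 1%, a 2-point excess at all six times, and the last three readings missing:

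- Complete-case repeated measures analysis: the donor is gone and none of the 0.08 is recovered.
- Tests at each time: 0.08 is kept at three times and 0 at the other three, a mean of (3 × 0.08 + 3 × 0)/6 = 0.04.
- If the excess occurs only in the missing readings: nothing is recovered by either route.

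**The case against.** The strongest reply is that the item is a non-evaluability rule: a delirious donor cannot give a trustworthy pain or anxiety score. That stands for affected VAS and postoperative BAI readings, and it justifies treating those as missing. It does not reach the 19 other readings, the opioid and antiemetic data, or VAS scores given before onset.

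A second reply is that the effect is negligible. Donors are ASA I–II, with neurological disorders and known psychiatric illness excluded, and every input to the size is assumed. Most of this stands: the shift is probably small and its direction is unknown. Larger values can be produced by combining a 10% risk with very different excesses in the two arms, but nothing in the documents supports such inputs. Even at zero shift, the analysed groups would be selected after randomisation.

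A third reply is that this is simply the per-protocol problem. Much of the harm does run through that sentence. But if only the sentence were changed, the criterion would still allow these donors to be called ineligible and removed.

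A reader might also infer that the plan orders the removal of delirious donors, or that the session changes delirium risk and so biases the trial in a known direction. The documents support neither. They never state the removal in words, and they give no evidence of an effect on delirium.

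**Conclusion.** The point holds as a defect in how the analysis set is determined, not as a demonstrated numerical error. The order of events and the per-protocol-only sentence are explicit, and nothing elsewhere keeps affected donors in. That they would be removed is an inference from these two statements, though the natural one.

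The numerical consequence cannot be known from the documents. The range of 0 to 0.15 VAS points, in either direction, rests on an assumed risk gap of at most 5 percentage points and an assumed excess of 1 to 3 points common to both arms. Confidence is high on the sequence and low on the size. The plan should be corrected because the fault is avoidable at little cost.

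**What to change.** 1. Delete the item from the exclusion criteria and treat delirium as a post-randomisation event.
2. Make the primary analysis all randomised donors in their assigned arm, using every reading obtained. Keep per-protocol as a sensitivity analysis.
3. Treat as missing only VAS and BAI readings that could not be obtained, and keep all other data from those donors.
4. For VAS, name a method that keeps donors with incomplete readings: a mixed model, or the planned two-group tests at each time.
5. Report by arm any clinically recorded delirium and any donors already removed for it, and restore their available data.

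A sensitivity analysis that shifts missing VAS values by different amounts in the two arms is optional.

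**Cost.** Protocol and SAP wording, a little more analysis and, if collection is still open, one data field for the reason a reading is missing. Section 10 gives study completion as November 1, 2024. If collection has closed, that field can no longer be filled at the time of the reading; on the data side, only restoring and reporting are possible. Delirium counts would be limited to what was clinically recorded. The change recovers only the part of the shift carried by readings actually obtained.

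### The primary VAS outcome at six times has no named deciding comparison, so the type I error of the primary claim is undefined, and the listed non-normal repeated-measures test cannot compare the arms

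*Combined protocol and SAP*

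**What the plan says.** The primary objective (section 2) is the effect of the consultation on "postoperative pain scores measured via the Visual Analog Scale (VAS) at predefined postoperative time points". No time is singled out. Section 6 lists the six times: "Time Frame: Postoperative 30 minutes, 2 hours, 6 hours, 12 hours, 24 hours, and 48 hours". Section 7 adds only the instrument: "Pain scores will be evaluated using a 10 cm Visual Analog Scale".

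Section 8 is organised by type of variable, not by outcome. The lines that could apply to VAS are:

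- "Continuous variables with normal distribution: Independent samples t-test"
- "Non-normal distribution: Mann-Whitney U test"
- "Repeated measurements: Repeated Measures ANOVA or Friedman test"

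One significance threshold of 0.05 covers everything. Section 8 does not link any test to VAS or define a per-patient summary. It does not say which ANOVA term is of interest, how sphericity is handled, what counts as success on the primary outcome, or how multiple tests are adjusted. No other section supplies these.

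**The concern.** Six scores per patient and several candidate tests allow several different primary results. A reader cannot tell which of them would have answered the primary objective, or at what error rate.

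There are two separate gaps.

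- **No deciding comparison.** On the ANOVA route, either the group effect or the group-by-time effect could be reported as the primary finding. The t-test and Mann-Whitney could be applied at each time or once to a per-patient summary, and the plan does not say which.
- **A listed test that does not address the objective.** If VAS is judged non-normal, the repeated-measures line leads to Friedman. That test asks whether scores change over time within patients. Following the plan to the letter on this route gives a p-value that says nothing about the intervention.

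What is at stake is how to read a positive result. If the six times were tested separately, a lone p just under 0.05 would be weak evidence, because Bonferroni over six tests would require p below about 0.0083.

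**Working it through.** The plan states no sample size, power or overall error rate, so there is no figure of its own to reproduce.

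**Inputs from the documents.** Two arms (section 3), six primary times (section 6) and a threshold of 0.05 (section 8).

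**Assumed, because the documents do not give them.** Two-sided tests. Between-time correlation r from 0.3 to 0.9, either exchangeable or AR(1) with r between adjacent times. Normal data with 25 or 50 per arm for the patient-level simulations (20,000 null trials per setting).

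**1. One named between-arm test decides.** The error is 0.05 by construction. The simulated ANOVA group effect rejected in about 4.6–5.4% of null trials.

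**2. Group-by-time alone decides, no sphericity correction.** About 5% under exchangeable correlation. Under AR(1) it rises from about 5.5% at r = 0.3 to about 9% at r = 0.9.

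**3. Either group or group-by-time counts, no sphericity correction.** About 9.4–10.1% exchangeable. Under AR(1), about 10% at r = 0.3 rising to about 13–14% at r = 0.9. With Greenhouse-Geisser correction it is about 9–10%.

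**4. Any one of six times counts.**

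- Independent scores: 1 − (1 − 0.05)^6 = 1 − 0.95^6 = 0.265.
- Correlated scores: 1 − P(all six |Z| ≤ 1.96), by numerical integration for the exchangeable case and 1,000,000 draws for AR(1).

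| r | Exchangeable | AR(1) |
|---|---|---|
| 0.3 | 24.1% | 25.4% |
| 0.5 | 20.7% | 23.5% |
| 0.7 | 16.4% | 19.8% |
| 0.9 | 10.8% | 13.3% |

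The Bonferroni level is 0.05/6 = 0.0083.

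**5. All six times required, in the same direction.** At most about 1.5% (exchangeable 0.9), so an undefined rule can also make the test conservative.

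**6. What a mean contrast costs in power.** Take an assumed effect of 0.6 SD and exchangeable r. The mean of six unit-variance scores has SD √((1 + 5r)/6): √(2.5/6) = 0.645 at r = 0.3 and √(5.5/6) = 0.957 at r = 0.9. Power from the noncentral t:

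| Situation | 25 per arm | 50 per arm |
|---|---|---|
| Effect at one time only, that time named in advance | 55% | 84% |
| Effect at one time only, mean contrast (mean shift 0.6/6 = 0.1) | 7–8% | 8–12% |
| Effect at all six times, mean contrast | 58–90% | 87% to over 99% |

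**7. Weighting.** An equal-weight mean gives the first three times 3/6 = 50% of the weight. Under a trapezoidal AUC from 0.5 to 48 h (47.5 h in all), their weights are 0.75 + 2.75 + 5 = 8.5 h, and 8.5/47.5 = 18%.

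**The case against.** The best defence is that six VAS scores are plainly repeated measurements and section 8 lists repeated-measures ANOVA for such data. If its group effect is the primary test, the error is about 5% and nothing is inflated. This stands as far as it goes: ANOVA is the natural reading. It does not close the gap. The line offers Friedman as the alternative, is not tied to VAS, and does not say which ANOVA term decides.

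Two stronger readings are tempting and should be resisted.

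- A reader might infer that the trial runs at a type I error of up to about 25%. The documents do not say that one significant time would be enough, so that figure belongs to a rule that is neither stated nor excluded. It also depends on an assumed correlation and its structure.
- A reader might infer that the non-normal route commits the trial to six Mann-Whitney tests. It does not. Mann-Whitney on a per-patient summary is a single test, and the plan does not say how it would be applied.

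It is also fair to say that no particular contrast is required. A single pre-named time, an AUC or an equal-weight mean would each fix the error at 5%, and the documents do not say which pain period matters most.

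**Conclusion.** The concern holds in this form: the primary claim has no defined decision rule, so its type I error is undefined rather than shown to be inflated. The Friedman point needs no numerical assumption. That test cannot compare two arms, so one route through the plan fails to answer the primary objective. This is why the matter goes beyond missing detail and needs correcting.

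Confidence is high on the missing rule and on Friedman. The percentages deserve less weight. They are scenario figures under assumed correlations, normal data and two-sided tests, not bounds. They show that the unresolved choices move the error from 5% to roughly two to five times that level, or well below it if all six times had to be significant.

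**What to change.** Name one primary between-arm contrast, tested once at two-sided 0.05, and state that Friedman will not be used to compare arms.

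- **Contrast.** One suitable choice is the difference in each patient's equal-weight mean VAS over the six times, which with complete data is the repeated-measures ANOVA group effect. A time-weighted AUC or one pre-named time would serve equally well for error control. Because the times are unevenly spaced, the weighting should be justified.
- **Method.** Fix one estimation method in advance, so that neither a normality test nor a missing value changes the primary analysis. For example, estimate the mean difference with a 95% CI from a mixed model (arm, time, arm-by-time, unstructured covariance) on all observed values, whether or not data are missing or non-normal. Keep a rank-based analysis of the per-patient mean as sensitivity only.
- **Everything else.** Make group-by-time (Greenhouse-Geisser corrected) and the six time-specific comparisons secondary, either Holm-adjusted or descriptive.

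**Cost.** No new data, only plan wording. With a mean contrast, an effect confined to one time can no longer carry the primary claim, and the power table above shows how much is given up in that case.

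**Timing.** Section 10 gives "Primary completion: October 1, 2024". If between-arm results have already been seen, the choice should be dated and reported as post hoc.

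### The only preoperative BAI falls after allocation and after the session, so anxiety has no baseline: comparisons of level stay valid, but precision is given up and a change or group-by-time reading could mislead

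*Combined protocol and SAP*

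**What the plan says.** Section 6 (Secondary Outcomes) gives the BAI schedule as "Time Frame: 30 minutes preoperatively, postoperative 24 hours, postoperative 48 hours". No section lists an earlier BAI.

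Section 5 places the intervention before that first score: "Participants received a standardized 15-minute psychiatric session one hour before surgery under psychiatrist supervision". Its four components are allotted 3–5, 3–5, 1–3 and 3–5 minutes. Section 3 places allocation earlier still: "Randomization was performed via sealed envelopes during preoperative evaluation".

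The anxiety objective in Section 2 is "To compare preoperative and postoperative anxiety levels between intervention and control groups". Section 8 offers "Continuous variables with normal distribution: Independent samples t-test", with Mann-Whitney U when the distribution is not normal, and "Repeated measurements: Repeated Measures ANOVA or Friedman test". It names no covariate, no baseline, and no term of the repeated-measures analysis that is to answer the objective.

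**The concern.** The session acts most directly on anxiety, so the BAI is where an effect would be expected first. A score labelled preoperative, followed by two postoperative scores, is easily taken for a baseline. Here it is not one, because the session has already been given when it is taken.

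Two things are at stake. First, without a pre-allocation score, baseline anxiety cannot be described by arm and the BAI comparison cannot be adjusted for it. Second, Section 8 leaves open how the repeated measures will be read. An analyst who reports the group-by-time term, or change from −30 min, would subtract whatever the session had already achieved by then. A lasting benefit could then be reported as no effect.

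**Working it through.** The documents give no BAI effect, SD, correlation or sample size, so there is no planned figure to reproduce. Steps 1 and 2 need no such inputs. Steps 3 to 5 use assumed values, marked as such.

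**1. Order of events (Sections 3, 5, 6).** Only one arm receives the session, so allocation must precede it. The components sum to 3 + 3 + 1 + 3 = 10 minutes at least and 5 + 5 + 3 + 5 = 18 at most; the nominal length is 15.

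- Session starts at −60 min: it ends between −50 and −42 min, so the gap to the BAI is 12 to 20 minutes (15 nominal).
- Session ends at −60 min: the gap is 30 minutes.

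On either reading the −30 min score comes after both allocation and the session. No time window is stated, and both times are assumed to count from the same moment.

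**2. What each contrast estimates.** Let d(t) be the between-arm difference in mean BAI at time t.

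- Level at time t (t-test): d(t). Mann-Whitney U likewise compares the arms at time t.
- Group main effect: the average of d(−30), d(24 h) and d(48 h).
- Change from −30 min: d(t) − d(−30).
- Group-by-time: tests whether d is the same at all times.

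If d is equal at all three times, the change contrasts are exactly 0. The group-by-time test then rejects at its 0.05 level whatever the sample size. If the effect wanes, say −0.7, −0.35 and 0 SD (assumed), the 24 h change contrast is −0.35 − (−0.7) = +0.35 SD, the wrong sign for a real early benefit. If the effect first appears after −30 min, nothing is cancelled.

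**3. Illustration of cancellation.** Assumed: SD 8, effect −5 at all three times, compound symmetry, r = 0.3 / 0.5 / 0.7, two-sided 0.05, equal arms, 20,000 simulated trials per setting. Proportion of trials rejecting:

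| n per arm | Group-by-time | Group main effect |
|---|---|---|
| 20 | 0.051 / 0.049 / 0.049 | 0.752 / 0.656 / 0.572 |
| 30 | 0.049 / 0.050 / 0.051 | 0.904 / 0.836 / 0.760 |
| 50 | 0.049 / 0.050 / 0.049 | 0.989 / 0.969 / 0.932 |

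With a late-only effect of 0, −3 and −3 (r = 0.5, 30 per arm), group-by-time and the 24 h t-test each reject in 0.298 of trials.

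**4. The −30 min score as covariate.** With equal variances the adjusted effect is d(24 h) − r·d(−30). For a sustained −0.70 SD this is −0.70 × (1 − r) = −0.49, −0.35 or −0.21 SD at r = 0.3, 0.5 or 0.7. Adjustment for this score removes part of the effect.

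**5. Value of a true baseline.** Adjustment multiplies residual variance by 1 − r², equivalent to 1/(1 − r²) − 1 more donors for the BAI comparison:

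| Assumed r | 1 − r² | Equivalent extra donors |
|---|---|---|
| 0.1 | 0.99 | 1% |
| 0.3 | 0.91 | 10% |
| 0.5 | 0.75 | 33% |
| 0.7 | 0.51 | 96% |

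Under the assumptions of step 3, with 30 per arm, power at 24 h goes from about 0.67 unadjusted to 0.70, 0.78 or 0.91 at r = 0.3, 0.5 or 0.7.

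**6. How late it is.** Section 10 gives "Start of enrollment: November 1, 2023" and "Primary completion: October 1, 2024", which are 335 days apart. Several entries in Section 13 carry an access date of 30 July 2024, which is day 272 (272/335 = 81%). If the timeline was kept, at most 335 − 272 = 63 days (19%) remained when the text was finalised. Sections 3 and 5 also describe allocation and sessions in the past tense.

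**The case against.** The best defence is that no planned comparison of levels is broken. The objective compares anxiety levels between arms, and the listed t-test or Mann-Whitney U does that at each time without bias. The plan never calls the −30 min score a baseline, and it mentions no change score, covariate or group-by-time term. Cancellation needs both an analysis the plan does not name and an effect of similar size at all three times. All of this stands.

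It is also fair that the numbers are soft. The simulated 0.05 for group-by-time restates the test's level under a contrast set to zero and is not further evidence. The gain from adjustment depends on an unknown r across an unstated interval that includes a nephrectomy; at r = 0.1 it is negligible. The simulation used continuous normal scores. The BAI is bounded at 0–63, and donors with known psychiatric illness are excluded, so low, skewed scores are possible and were not examined.

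Two points survive. Section 8 leaves the repeated-measures term open, so the misleading reading is available although not chosen. And its Friedman alternative has no between-arm factor: it can show change over time within an arm, but it cannot answer a between-arm objective.

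A reader might infer that the BAI comparison is biased, or that the trial cannot detect an anxiety effect. The documents support neither: randomisation protects the comparison without a baseline, and the group main effect and the tests at each time would detect a sustained difference.

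**Conclusion.** The point holds as a cheap improvement and a matter of specification, not as an error that invalidates an analysis. On nominal times, anxiety has no pre-allocation score, and the −30 min BAI is an early outcome. An unlisted BAI at the preoperative evaluation cannot be excluded, but none is planned.

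The certain loss is a description of baseline anxiety. The loss of precision runs from almost nothing to about half the residual variance over an assumed r of 0.1 to 0.7. The cancellation is exact for a constant effect, but conditional on reading the analysis through group-by-time or change from −30 min. The reach is one of the eight secondary outcomes in Section 6; the primary VAS outcome is not touched.

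**What to change.** For donors not yet allocated, give the BAI at the preoperative evaluation, before the envelope is opened. Compare the arms at −30 min, 24 h and 48 h in one mixed model or ANCOVA adjusted for that score, and state in advance which between-arm contrast answers the objective.

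Keep donors already treated without that score in the same analysis. One way is a longitudinal model with the pre-allocation BAI as a further response, a common mean for both arms at that time, and arm-specific means afterwards. Donors without the score contribute their three later values. Whether it is missing depends on the date of enrolment, not on the donor's anxiety.

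State that the −30 min score will not serve as baseline, covariate or change reference, and do not use Friedman to compare arms. If the scores are clearly not normal, the listed Mann-Whitney U at each time remains a valid between-arm test.

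If enrolment is over, say that no baseline exists and base BAI inference on between-arm levels at each time or on the group main effect. This costs nothing if settled before the BAI data are analysed, but it does not recover the precision.

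The cost of the extra score is one questionnaire per donor at an evaluation that already takes place, and it may come too late for most donors.
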